**LEGEND FOR ALL STUDY CALENDARS:**

- A:** Dorgenmeltucel-L (HyperAcute-Melanoma), 300 million HAM cells administered intradermally
  - B:** Serum chemistries including BUN, creatinine, calcium, albumin, glucose, electrolytes, liver function tests including total bilirubin, ALT (SGPT) AST (SGOT), alkaline phosphatase and LDH. Should be drawn at the first follow-up visit and then as clinically indicated when subjects are in follow-up.
  - C:** Serum or urine pregnancy test (Women of childbearing potential).
  - E:** [REDACTED]
  - F:** **For subjects receiving HAM immunotherapy:** Peripheral blood collection (10 mL purple top tube provided by NewLink Genetics) is to be sent same day, on room air, overnight express to NewLink Genetics for RCR testing for retrovirus. Draw prior to first immunization (Day 1) only.
  - H:** [REDACTED]
  - I:** [REDACTED]
  - J:** [REDACTED]
- 1ST FUV:** Please complete all procedures as outlined in the study calendars under 1st FUV.

**Study Calendar for Arm 2A (Ipilimumab Alone)**

Ipilimumab 3 mg/kg IV given Q3 weeks x 4, then evaluate disease. Study visits may be performed +/- 3 days from the targeted study visit date to allow for holidays and other scheduling conflicts. Follow-up visits may be performed +/- 2 weeks from the targeted study visit date.

EVALUATIONS	Pre-Study	Wk 1	Wk 2	Wk 3	Wk 4	Wk 5	Wk 6	Wk 7	Wk 8	Wk 9	Wk 10	Wk 11	Wk 12	Wk 13	1ST FUV
		D1	D8	D15	D22	D29	D36	D43	D50	D57	D64	D71	D78	D85	
Ipilimumab		X			X			X			X				
Informed consent	X														
Demographics	X														
Medical history	X														
Concurrent meds	X	X-----X													
Physical exam	X	X			X			X			X				X
Vital signs	X	X			X			X			X			X	X
Height	X														
Weight	X	X			X			X			X				X
Performance status	X	X			X			X			X			X	X
CBC w/diff, plts	X	X			X			X			X			X	X
Serum chemistry (with LDH)	B	B			B			B			B			B	B
B-HCG	C														
TSH and Free T4	X	X			X			X			X			X	
		E												E	E
		H						H							H
		I			I			I			I			I	I
		J						J			J				
Radiologic Tumor (RECIST/iRRC) evaluation	X													X	X
Adverse event evaluation		X-----X													X

**Study Calendar for Arm 2B (Nivolumab Alone)**

Nivolumab 240 mg Q2 weeks until disease progression or significant toxicity Study visits may be performed +/- 3 days from the targeted study visit date to allow for holidays and other scheduling conflicts. Follow-up visits may be performed +/- 2 weeks from the targeted study visit date.

EVALUATIONS	Pre-Study	Wk 1	Wk 2	Wk 3	Wk 4	Wk 5	Wk 6	Wk 7	Wk 8	Wk 9	Wk 10	Wk 11	Wk 12	Wk 13	1ST FUV
		D1	D8	D15	D22	D29	D36	D43	D50	D57	D64	D71	D78	D85	
Nivolumab		X		X		X		X		X		X		X	
Informed consent	X														
Demographics	X														
Medical history	X														
Concurrent meds	X	X-----X													
Physical exam	X	X													X
Vital signs	X	X		X		X		X		X		X		X	X
Height	X														
Weight	X	X				X				X				X	X
Performance status	X	X		X		X		X		X		X		X	X
CBC w/diff, plts	X	X		X		X		X		X		X		X	X
Serum chemistry (with LDH)	B	B		B		B		B		B		B		B	C
B-HCG	C														
TSH and Free T4	X	X				X				X				X	
		E												E	E
		H						H							H
		I		I		I				I				I	I
		J						J				J			
Tumor measurements	X													X	X
Radiologic (RECIST/iRRc) evaluation	X													X	X
Adverse event evaluation		X-----X													X

**Each Subsequent Cycle:**

**Days 1 and 15** – Nivolumab 240 mg given IV; Obtain VS, PS, CBC, Chemistries

**Day 1** – TSH and Free T4, [REDACTED] (monthly x 8, every 3 months x 4), Weight

**Study Calendar for Arm 1C (Pembrolizumab plus Dorgenmeltucel-L)**

Pembrolizumab 2 mg/kg given Q3 weeks until disease progression or significant toxicity, dorgenmeltucel-L continues for up to 24 immunizations. Study visits may be performed +/- 3 days from the targeted study visit date to allow for holidays and other scheduling conflicts. Follow-up visits may be performed +/- 2 weeks from the targeted study visit date.

EVALUATIONS	Pre-Study DAY	Wk 1	Wk 2	Wk 3	Wk 4	Wk 5	Wk 6	Wk 7	Wk 8	Wk 9	Wk 10	Wk 11	Wk 12	Wk 13	Wk 14	Wk 16	Wk 18	Wk 20	Wk 22	Wk 24	Mo 7	Mo 8	Mo 9	Mo 10	Mo 11	Mo 12	Mo 15	Mo 18	Mo 21	Mo 24	1ST FUV			
HAM Injections		A	A	A	A		A		A		A		A		A	A	A	A	A	A	A	A	A	A	A	A	A	A	A	A				
Pembrolizumab				X			X			X			X	-----Continue Pembrolizumab every 3 weeks-----																				
Informed consent	X																																	
Demographics	X																																	
Medical history	X																																	
Concurrent meds	X	X-----X																																
Physical exam	X	X		X			X			X			X		X		X		X		-----Complete per SOC-----													X
Vital signs	X	X	X	X	X		X	X	X		X		X	X	X	X	X	X	X	X	X	X	X	X	X	X	X	X	X	X	X	X		
Height	X																																	
Weight	X	X		X			X			X			X		X		X		X		X	X	X	X	X	X	X	X	X	X	X			
Performance status	X	X		X			X			X			X		X		X		X		X	X	X	X	X	X	X	X	X	X	X			
CBC w/diff, plts	X	X		X			X			X			X		X		X		X		X	X	X	X	X	X	X	X	X	X	X			
Serum chemistry (with LDH)	B			B			B			B			B		B		B		B		B	B	B	B	B	B	B	B	B	B	B			
b-HCG	C																																	
TSH and Free T4	X			X			X			X			X		X		X		X		----Obtain at least monthly during Pembrolizumab													
	E																				E					E			E	E				
	F																																	
	H						H						H				H				H			H		H		H	H	H				
	I		I	I			I			I			I			I		I		I		I	I	I	I	I	I	I	I	I	I			
	J						J			J			J																					
Radiologic Tumor (RECIST/iRRC) evaluation	X												X							X			X			X	X	X	X	X	X			
AE/SAE Evaluation		-----Evaluate throughout Study and Follow Up Per Protocol-----																																

**Each Subsequent Cycle:**

- Pembrolizumab 2 mg/kg IV given every 3 weeks
- VS, PS, CBC, Chemistries completed every 3 weeks while receiving Pembrolizumab
- TSH and Free T4 completed at least monthly while receiving Pembrolizumab
- [REDACTED]
- Imaging for disease evaluation completed every 3 months

**Study Calendar for Arm 2C (Pembrolizumab Alone)**

Pembrolizumab 2 mg/kg given Q3 weeks until disease progression or significant toxicity. Study visits may be performed +/- 3 days from the targeted study visit date to allow for holidays and other scheduling conflicts. Follow-up visits may be performed +/- 2 weeks from the targeted study visit date.

EVALUATIONS	Pre-Study	Wk 1	Wk 2	Wk 3	Wk 4	Wk 5	Wk 6	Wk 7	Wk 8	Wk 9	Wk 10	Wk 11	Wk 12	Wk 13	1ST FUV
		D1	D8	D15	D22	D29	D36	D43	D50	D57	D64	D71	D78	D85	
Pembrolizumab		X			X			X			X			X	
Informed consent	X														
Demographics	X														
Medical history	X														
Concurrent meds	X	X-----X													
Physical exam	X	X			X			X			X			X	X
Vital signs	X	X			X			X			X			X	X
Height	X														
Weight	X	X			X			X			X			X	X
Performance status	X	X			X			X			X			X	X
CBC w/diff, plts	X	X			X			X			X			X	X
Serum chemistry (with LDH)	B	B			B			B			B			B	B
B-HCG	C														
TSH and Free T4	X	X			X			X			X			X	
		E												E	E
		H						H							H
		I			I			I			I			I	I
		J						J			J				
Tumor measurements	X													X	X
Radiologic (RECIST/iRRc) evaluation	X													X	X
Adverse event evaluation		X-----X													X

**Each Subsequent Cycle:**

- Pembrolizumab 2 mg/kg IV given every 3 weeks
- VS, PS, CBC, Chemistries, TSH and Free T4, [REDACTED] (monthly x 8, every 3 months x 4)
- Imaging for disease evaluation completed every 3 months

**Follow Up Visits for ALL Subjects (after 1st FUV):**

- Imaging to be completed every 3 months until disease progression, after disease progression imaging is completed per standard of care
- Survival status checks to be completed at least every 3 months until death or lost to follow up
- All other assessments should be completed per standard of care practices.

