#### 4.4 *Duration of Therapy*

Patients whose tumor progresses on therapy will be off-study. However, mild progression ( $\leq 25\%$  increase in tumor size) at the beginning of the treatment is allowed, given the usual delayed response / pseudoproggression seen with immunotherapy (Wolchok et al., 2009).

Patients who experience a SAE which triggers stopping rules for immune checkpoint inhibitors ipilimumab, nivolumab, or pembrolizumab as described in their respective package inserts will be permanently discontinued from the immune checkpoint inhibitor. They can be continued on dorgenmeltucel-L (if in Arm 1) once recovered from immune checkpoint inhibitor toxicity.

Patients are also off study who:

- experience intercurrent illness that prevents further administration of treatment;
- decide to withdraw from the study;
- experience general or specific changes in the patient's condition that render them unacceptable for further treatment in the judgment of the investigator.

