### Immune-related Endpoints

The irRC incorporates several elements reflecting the complex tumor dynamics of ipilimumab treatment. Under these criteria, a measure of tumor volume is used that incorporates the contribution of new measurable lesions. Each net percentage change in tumor burden per assessment using irRC accounts for the size and growth kinetics of both old and new lesions as they appear. New lesions alone do not qualify as irPD.

In this study, irRC will be used to assess subject response to study treatment per investigator assessment. The endpoint irPFS will be determined based on investigator assessment. In order to adequately address this objective, investigators will obtain confirmatory scans beyond RECIST PD and follow the instructions in this section for the determination of immune-related response.

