### New Lesion Measurement

The irRC are tumor assessment criteria that have been developed to better capture the activity of immunotherapeutic agents. These criteria have been used with success in clinical studies that were performed with ipilimumab in advanced metastatic melanoma and in lung cancer.

Additional tumor response data will be collected, beyond what is required to apply the RECIST criteria. More specifically, the investigator will have to record in the CRF the bi-dimensional measurements for each new lesion which has become measurable in each tumor assessment.

To support evaluation of progression-free survival based on irRC criteria (irPFS) in this indication, investigators must perform tumor assessments (including new lesion measurements) during the Toxicity/Progression Follow-up Phase in subjects who have experienced RECIST progression until the total sum of product diameters (SPD including new lesions) has increased 25% or more from the nadir or until subjects discontinue study therapy regardless of whether the subject is initiating subsequent therapy. All available post RECIST progression tumor imaging- based assessments during this phase in the study must be entered into the CRF, including any standard of care assessments and any assessments performed while under non-study subsequent cancer therapy.

Any subject who develops an objective tumor response (CR or PR) or progression (PD) is required to undergo confirmatory scans no less than 4 weeks since the prior scan in order to verify the reliability of the radiologic finding. Sites are encouraged to collect additional CT scans after RECIST PD has been confirmed, as long as a subsequent line of therapy has not been initiated.

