### **Efficacy Analyses**

The primary efficacy endpoint is PFS, where disease progression is defined according to RECIST v1.1. Progression free survival will be summarized using the Kaplan-Meier method of estimation, including the 25th, 50th, and 75th percentiles of time to progression with 95% confidence intervals. Kaplan-Meier plots will be produced by disease status strata to examine the difference in response rates between treatment groups. A stratified log rank test will be applied to test for treatment effect on PFS.

Overall response rate is defined as subjects with a best overall response of at least stable disease. Subjects' best overall response, as determined by the investigator from RECIST, will be summarized by presenting the numbers and percentages of subjects in each response category. The overall response rate will be summarized similarly. Ninety-five percent confidence intervals (CIs) will be constructed for the overall response rate.

The duration of overall response is measured from the time measurement criteria are met for CR or PR (whichever is first recorded) according to RECIST v1.1 until the first date that recurrent or progressive disease is objectively documented (taking as reference for progressive disease the smallest measurements recorded since the treatment started). Duration of overall response will be analyzed in a similar manner to PFS.

Duration of stable disease is measured from the start of the treatment until the criteria for progression are met according to RECIST v1.1, taking as reference the smallest measurements recorded since the treatment started, including the baseline measurements. Duration of stable disease will be analyzed in a similar manner to PFS.

Overall survival is defined as the time to death or last contact and will be summarized in a similar manner to PFS.

As additional secondary endpoints, analysis of PFS, overall response rate, duration of overall response, and duration of stable disease will be repeated using the irRC criteria to identify disease response.

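### The rules for imaging after RECIST progression conflict, so irPFS and the other irRC endpoints may be ascertained incompletely and, mainly in the ipilimumab pair, unequally between arms

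*Combined protocol and SAP*

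**What the plan says.** Section 9.1 (Immune-related Endpoints) states that, to address irPFS, "investigators will obtain confirmatory scans beyond RECIST PD". Under New Lesion Measurement, any subject with an objective response or progression "is required to undergo confirmatory scans no less than 4 weeks since the prior scan". The same subsection makes tumor assessments after RECIST progression mandatory until the sum of products, counting new lesions, is at least 25% above its lowest value. It adds an alternative stop: "until subjects discontinue study therapy regardless of whether the subject is initiating subsequent therapy". It then only encourages further CT scans once RECIST progression is confirmed, and only before a new line of therapy. Any post-progression images that exist, standard-of-care scans included, must be entered in the CRF.

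Other sections differ. Section 8 (Follow Up Visits for ALL Subjects) sets imaging every 3 months up to progression, but "after disease progression imaging is completed per standard of care". Section 4.4 says "Patients whose tumor progresses on therapy will be off-study", with an allowance for early growth of up to 25%. The schemas for Arms 2A, 2B and 2C take progressing subjects off study and keep only survival status.

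Section 12.3 lists as additional secondary endpoints that PFS, response rate, and the durations of response and stable disease "will be repeated using the irRC criteria to identify disease response".

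**The concern.** Under irRC, a new lesion alone is not progression. A patient with RECIST progression through a new lesion may therefore still be free of irPD, and only later measured scans can show when, or whether, irPD occurs. A site that follows the calendar, Section 4.4 or the Arm 2 schemas has no scheduled occasion to obtain those scans.

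Two problems follow. First, imaging becomes a matter of clinical judgment. Whether a patient is scanned again then depends on how that patient is doing, and censoring at the last scan is no longer independent of prognosis. Second, the duty to continue serial scans is tied to study therapy, whose planned length is not the same in both arms of every pair. The irRC endpoints exist to capture delayed response, so they are the endpoints most exposed to uneven follow-up after RECIST progression.

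**Working it through.** **1. The plan's own figure.** No design figure is given for irPFS. The only PFS figure is the 96 events in Section 12.1, for the primary endpoint (two-sided alpha 0.20). Freedman's formula for 1:1 allocation is d = (z₁₋α/₂ + z_power)² × [(1 + HR)/(1 − HR)]².
- 80% power, HR 0.6435: (1.2816 + 0.8416)² × (1.6435/0.3565)² = 4.508 × 21.25 = 95.8, so 96.
- 70% power, HR 0.6895: (1.2816 + 0.5244)² × (1.6895/0.3105)² = 3.262 × 29.61 = 96.6, so 97.

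The figure reproduces, and this point does not alter it. It does show the reach of the rule. With 96 events planned in 100 patients, nearly every patient whose event is not a death will come under the post-progression instructions.

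**2. What irPFS needs.** Section 9.1 defines irPD as a rise of at least 25% in irSPD over its nadir, or any new measurable lesion if the SPD nadir is zero. A patient with a non-zero nadir and a new lesion needs later measurements. A patient with no measurable disease at baseline reaches irPD with the first new measurable lesion, and later scans matter less.

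**3. The instructions side by side.**

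| Place | After RECIST progression |
|---|---|
| 9.1, confirmatory scan | Required of any subject, at least 4 weeks after the prior scan |
| 9.1, serial assessments | Required until the 25% rise or the end of study therapy |
| 9.1, additional CT scans | Encouraged, before subsequent therapy only |
| 8, all subjects after the first follow-up visit | Standard of care |
| 4.4, all arms | Off study, except early mild progression |
| Arm 2A, 2B and 2C schemas | Off study, survival status only |

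A site cannot follow all of these. The Toxicity/Progression Follow-up Phase, in which Section 9.1 places the serial scans, is not defined in the text supplied.

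**4. Planned therapy length against scan dates.**
- Arm 2A: doses on Days 1, 22, 43 and 64. The first response evaluation follows week 12 (which starts on Day 78) in the schema and is on Day 85 in the calendar. That is at least 78 − 64 = 14 days, or 85 − 64 = 21 days, after the last planned dose.
- Arm 1A: 14 immunizations to week 24, 6 in months 7 to 12, and 4 at months 15, 18, 21 and 24, which makes 24. Eight response evaluations fall in that span.
- Pairs B and C: the checkpoint inhibitor runs until progression or significant toxicity in the monotherapy arms and continues in the combination arms. No difference in length is built into the checkpoint schedule.
- Any pair: Section 4.4 lets Arm 1 patients stay on dorgenmeltucel-L after stopping the checkpoint inhibitor for toxicity. Arm 2 has no counterpart.

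**5. Combining the stop clause with Section 4.4.** At clear progression, Section 4.4 (with 4.5) ends study therapy in both arms, so the serial-scan duty lapses in both. The arms can differ in two situations. One is early mild progression in the ipilimumab pair, where Arm 1A still has planned therapy and Arm 2A has none left. The other is vaccine continued after checkpoint-inhibitor toxicity, in any pair.

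**6. Size.** A calculation would need the share of patients on ipilimumab, the share of RECIST progressions that are not yet irPD, the delay to irPD, and the irPFS censoring rule. None is given in the text supplied. Section 12.3 (Missing Data) leaves endpoint-specific imputation rules to the statistical analysis plan.

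**The case against.** The case against has real force.

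- **Deferral to irRC.** Section 9.1, under non-target lesions, says that suspected progression with less than a 25% increase, or with new lesions, does not count at once and goes to irRC evaluation. On that reading these patients have not progressed, and 3-monthly imaging continues in every arm. This narrows the group affected. It does not settle the matter, because the RECIST definitions in the same section count a new lesion as progression, and Section 8 does not say which progression it means.
- **Capture in the CRF.** Standard-of-care scans must be recorded, so Section 8 weakens the imaging schedule and does not abolish it. That stands. Recording whatever was done still does not ensure that a scan was done.
- **The Arm 2A reading is not the only one.** Completing four doses is not plainly discontinuing therapy, the named follow-up phase suggests scans after treatment, and Section 6.3 lets delayed ipilimumab run to 16 weeks from the first dose, beyond Day 85. All fair; the timing in step 4 is the undelayed schedule.
- **Limited scope and consequence.** A built-in difference in therapy length exists in one pair of three, and Section 2.5 notes a shift toward PD-1 inhibitors. The irRC endpoints are not formally tested. Both points stand.

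A reader might infer that irRC results are not comparable between arms, or attach a spurious hazard ratio to the problem. The documents support neither. The confirmatory scan applies to any subject, Section 4.4 stops both arms at clear progression, and a hazard ratio would rest on unsourced proportions and delays and on a censoring rule the plan does not state. Even its direction would depend on the assumed delay to irPD.

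**Conclusion.** The contradiction is established by the text: Section 9.1 requires scans that Sections 4.4 and 8 and the Arm 2 schemas do not provide for. Without them, irPFS and the other irRC endpoints cannot be determined reliably in patients whose RECIST progression is not yet irPD. The therapy-linked stop adds a risk of differential ascertainment and informative censoring, mainly in the ipilimumab stratum and to a lesser extent wherever vaccine continues after checkpoint-inhibitor toxicity.

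The Arm 1A versus 2A contrast assumes the undelayed dosing schedule and treats completion of the four doses as the end of study therapy. The size and direction of any bias remain unknown. The primary RECIST v1.1 analysis and its 96 events are not in question. Biased irRC estimates would nevertheless be reported and read even without a test, so the text is worth correcting.

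**What to change.** 1. Reconcile Section 4.4, Section 8 and the Arm 2 schemas with Section 9.1, including its deferral of new lesions and small increases to irRC. The confirmatory scan at least 4 weeks after RECIST progression should be done in every arm, whether or not the patient is still on therapy. This concerns assessment only and takes no position on when treatment should stop.
2. Replace the therapy-linked stop with one end to post-progression assessment that is the same in both arms and does not depend on treatment. Deleting the clause alone is not enough, because scanning would then be open-ended until the 25% rise. Define the follow-up phase that the text names, and resolve the required and encouraged wording.
3. State the irPFS censoring rule that matches this schedule, including patients with no scan after RECIST progression and those who start subsequent therapy.
4. If these changes are not made, report irPFS descriptively by arm and omit the between-arm comparison.

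The cost is mostly wording. In practice, some patients off therapy must return for a scan that Section 9.1 already requires. Any assessments beyond that scan depend on the end point chosen in item 2.

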## 9 MEASUREMENT OF EFFECT

### 9.1 *Antitumor Effect – Solid Tumors*

Each time a tumor assessment occurs, response and progression will be evaluated in this study using both the new international criteria proposed by the revised Response Evaluation Criteria in Solid Tumors (RECIST) guideline (version 1.1) [*Eur J Ca* 45:228-247, 2009] as well as immune-related response criteria (irRC). Changes in the largest diameter (unidimensional measurement) of the tumor lesions and the shortest diameter in the case of malignant lymph nodes are used in the RECIST criteria. Criteria for immune-related response criteria are described later in this section.

Tumor assessments will be performed approximately every 3 months in all treatment arms.

#### **Definitions**

Evaluable for toxicity: All patients will be evaluable for toxicity from the time of their first treatment with ipilimumab or dorgenmeltucel-L.

Evaluable for objective response: Only those patients who have measurable disease present at baseline, have received at least one cycle of therapy, and have had their disease re-evaluated will be considered evaluable for response. These patients will have their response classified according to the definitions stated below. (Note: Patients who exhibit objective disease progression prior to the end of cycle 1 will also be considered evaluable.)

Evaluable Non-Target Disease Response: Patients who have lesions present at baseline that are evaluable but do not meet the definitions of measurable disease, have received at least one cycle of therapy, and have had their disease re-evaluated will be considered evaluable for non-target disease. The response assessment is based on the presence, absence, or unequivocal progression of the lesions.

